# 7.14.7 T Lymphocyte Repertoire

To assess changes in T cell clonality and diversity in response to flotetuzumab, IgH and TCR from genomic DNA will be amplified using universal primer sets and quantify the frequency of clones using next-generation sequencing. CDR3 sequences will also be analyzed for clonotype across patients.

# 7.14.8 Sample Collection, Storage, and Shipping

For samples to be analyzed at a central laboratory, sample collection, handling, labeling, and shipping procedures are described in the Laboratory Manual.

# 7.14.9 Sample Retention and Further Testing

Samples acquired for protocol specified assays will be retained for study purposes (analysis/re-analysis) and may be retained up to 2 years after last approval of a marketing application in an ICH region and until there are no pending or contemplated marketing applications in an ICH region or until at least 2 years have elapsed since formal discontinuation of clinical development of the investigational product. If patients consent to the use of their study samples for non-study research purposes, these samples may also be used for exploratory testing (including assay development/optimization) and may be retained up to 15 years from the end of study.

# 7.15 Appropriateness of Measurements

Routine laboratory evaluations including hematology, chemistry, special chemistry, coagulation, and urinalysis will be carried out in local institutional laboratories. Additional local safety laboratory assessments may be used to supplement the protocol-prescribed assessments and may be used to elucidate certain AEs. If during assessment of AEs a patient undergoes imaging study and/or sample collection, e.g., pleural fluid, intra-articular joint aspiration, or ascitic fluid, a sample may be provided to the Sponsor to help elucidate etiology.

Serum concentrations of flotetuzumab will be monitored. Standard bridging enzyme-linked immunosorbent assays (ELISAs) will be carried out in the Sponsor's designated central laboratory to characterize the immunogenicity of flotetuzumab. Analysis of PK data will be carried out using industry standard software. The impact of AML on PK parameters will be evaluated.

Baseline, on-treatment, and follow-up bone marrow aspiration and/or biopsy specimens will be used for the assessment of disease status and effects of flotetuzumab treatment. These

assessments will be carried out in routine fashion in the investigational institutions' facilities. Material may be requested for central review during or following completion of the study.

# 8 STUDY ACTIVITIES

A table of study activities by study day is presented in the Schedule of Events for Cohort Expansion (Appendix 1).

# 8.1 **Pre-treatment Evaluations**

Patients will be evaluated before registration. At this screening visit, patients will enter the study upon signing the study-specific informed consent document. Only those patients who meet all inclusion/exclusion criteria specified in Sections 5.1 and 5.2 will be enrolled. Informed consent must be obtained prior to performing any screening procedures and may be obtained prior to the start of the 14 day screening period.

# 8.1.1 Within 14 Days Before Treatment

The screening window will start with the conduct of the first pre-treatment evaluation.

Pre-treatment evaluations and activities include:

- Obtain bone marrow aspirate and/or biopsy specimen, if not performed within 30 days before the start of treatment (Cycle 1 Day 1), for local histopathological and immunohistochemical evaluation, central flow cytometric evaluation, and minimal residual disease analysis.
- Obtain buccal mucosal sample (only Washington University Site in St. Louis, MO).
- If patient has a history or signs and symptoms of cardiac disease, obtain echocardiogram (or, except in Germany, MUGA if indicated) if one was not performed within 30 days before the start of treatment (Cycle 1 Day 1). An echocardiogram (or, except in Germany, MUGA if indicated) may also be conducted during the study if clinically indicated.
- Conduct PFT, including DLCO and FEV1, if testing was not performed within 30 days before the start of treatment (Cycle 1 Day 1). PFT may also be conducted during the study if clinically indicated.
  - During the COVID-19 pandemic, except in Germany, if PFT equipment is not available to perform the required screening procedure, the recommended alternative is to perform a correlative stair-climbing test of 5 flights (127 steps), per Bolton (3). The patient is to walk up several flights of stairs at his/her own moderate pace (timed with a stopwatch) and encouraged to proceed as far as possible without stopping. The patient is considered passing the stair climb screening test if the patient can complete all 5 flights (127 steps) without complications, such as prolonged recovery time, severe air hunger, or stopping the climb due to non-pulmonary complaints. The site will be expected to provide baseline data (including pulse rate, blood pressure, and respiratory rate) obtained prior to the stair climb, documentation of the number of stairs the patient

was able to climb, time in seconds, reason for stopping, and the  $O_2$  saturation the patient achieved as described in Bolton et al. In addition, the pulse rate, blood pressure and respiratory rate should be recorded immediately post climb, at 2 minutes after stopping, at 5 minutes after stopping and at 10 minutes after stopping if the patient did not fully recover within 5 minutes. If the patient passes the stair climbing test, CT of the lung and echocardiogram, irrespective of cardiac history, must be performed.

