## 5 SELECTION AND WITHDRAWAL OF PATIENTS

#### 5.1 Inclusion Criteria

Each patient must meet all the following criteria to be enrolled in this study. No exceptions to these criteria can be granted by the Sponsor.

- 1. Patients must have a confirmed diagnosis of primary or secondary AML (any subtype except acute promyelocytic leukemia [APL]) according to World Health Organization (WHO) classification.
- 2. Patients with AML must meet one of the following criteria, a or b:
  - a. **Primary Induction Failure (PIF)** AML, defined as disease refractory to one of the following, i or ii:
    - i. An intensive induction attempt, per institution.

Induction attempts include high-dose and/or standard-dose cytarabine  $\pm$  an anthracyclines/anthracenedione  $\pm$  an anti-metabolite, with or without growth factor or targeted therapy containing regimens.

Examples include but are not limited to:

- 1. One cycle of high dose cytarabine (HiDAC) containing regimen
- 2. One cycle of liposomal cytarabine and daunorubicin
- 3. Two cycles of standard dose cytarabine containing regimen
- ii. For adults who are age 75 years or older, or who have comorbidities that preclude use of intensive induction chemotherapy; PIF is defined as AML refractory to one of the following less intensive regimens, 1 or 2:
  - 1.  $\geq$  2 but  $\leq$  4 cycles of Bcl-2 inhibitors in combination with azacitidine, decitabine, or low dose cytarabine
  - 2.  $\geq 2$  but  $\leq 4$  cycles of gemtuzumab ozogamicin monotherapy
- b. **Early relapse (ER)** AML, defined as AML in first relapse with initial CR1 duration < 6 months
- 3. Limit of 3 prior lines of therapy (excluding focal radiation therapy for palliative purposes): up to 2 induction (induction, re-induction) or 1 induction plus/minus 1 consolidation attempt, followed by a maximum of 1 salvage/re-induction attempt.
- 4. Eastern Cooperative Oncology Group (ECOG) performance status  $\leq 2$ .
- 5. Life expectancy of at least 4 weeks.
- 6. Peripheral blast count  $\leq 20,000/\text{mm}^3$  at the time of first dose of study treatment (see related **Exclusion Criterion 3**).
- 7. Adequate hepatic and renal function:

- a. hepatic transaminase (both alanine aminotransferase (ALT) and aspartate aminotransferase (AST) levels ≤ 2.5 times the institutional upper limit of normal (ULN),

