#### 5.2 Exclusion Criteria

Patients who meet any of the following criteria will be excluded from the study. No exceptions to these criteria can be granted by the Sponsor.

- 1. Prior history of allogeneic stem cell transplantation.
- 2. Prior treatment with an anti-CD123-directed agent.
- Need for concurrent other cytoreductive chemotherapy (use of hydroxyurea or other cytoreductive agents should have ceased by the time the study medication is begun (Cycle 1 Day 1) however, hydroxyurea may be reinstituted at the discretion of the Investigator for the prevention or treatment of signs or symptoms of leukostasis, see Section 6.6), i.e., the target peripheral blast count for inclusion in the study should be ≤ 20,000/mm^3 at the time of first dose of study treatment.
- 4. Any active untreated autoimmune disorders (with the exception of vitiligo, resolved childhood atopic dermatitis, prior Grave's disease now euthyroid clinically and with stable supplementation).
- 5. Second primary malignancy that requires active therapy. Adjuvant hormonal therapy is allowed.
- 6. Antitumor therapy (chemotherapy, radiotherapy, antibody therapy, moleculartargeted therapy, retinoid therapy, or investigational agent) within 14 days or 5 half-lives of Cycle 1 Day 1, whichever is longer. Ruxolitinib is permitted for patients in the ruxolitinib mini-cohort.
- 7. Requirement, at the time of study entry, for concurrent steroids > 10 mg/day of oral prednisone or the equivalent, except steroid inhaler, otic preparations, nasal spray or ophthalmic solution.
- 8. Use of immunosuppressant medications (other than steroids as noted) in the 2 weeks prior to study drug administration (Cycle 1 Day 1).
- Use of granulocyte colony stimulating or granulocyte-macrophage colony stimulating factor in the 2 weeks prior to study drug administration (Cycle 1 Day 1).
- 10. Known central nervous system (CNS) leukemia. Patients with suspected CNS leukemia must be evaluated by lumbar puncture and be free of CNS disease prior to study entry. Previously treated CNS leukemia is allowed provided adequate treatment has been provided and the patient is free of CNS disease.

- 11. Any medical or psychiatric condition limiting full compliance or increasing the safety risk, such as:
  - a. active uncontrolled infection (including, but not limited to viral, bacterial, fungal, or mycobacterial infection),
  - b. known human immunodeficiency virus infection, unless all of the following criteria are met:

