# 6.6 Concomitant Therapy

All concomitant medications and blood products administered during the patient's participation in the study must be recorded in the source document and on the electronic Case Report Form (eCRF). Patients' blood product administered up to 28 days before enrollment should also be specified in the eCRF. Specifically, concomitant medications must be recorded through 7 days after the last administration of study drug or until the End-of-Treatment visit, whichever is later. Any concomitant medication associated with an AE or SAE that is

considered related to study drug must be recorded through 28 days after the last administration of study drug or End-of-Treatment visit, whichever is later.

Patients may not receive the following concurrent therapy:

- Any other therapies for leukemia. Use of hydroxyurea or other cytoreductive agents for the purposes of achieving an initial peripheral blast count ≤ 20,000/mm^3 should have ceased by the time of first dose of study treatment (Cycle 1 Day 1). However, hydroxyurea may be reinstituted at the discretion of the Investigator for the prevention or treatment of signs or symptoms of leukostasis during the time of study participation.
- Previous treatment with any other investigational agent within 14 days or 5 halflives, whichever is longer, prior to study drug administration (Cycle 1 Day 1) is prohibited. Ruxolitinib is permitted for patients in the ruxolitinib mini-cohort.
- Patients may not receive other investigational drugs during the period of study participation.
- Because flotetuzumab employs a mechanism of action dependent upon the engagement of T lymphocytes, the use of corticosteroids other than those employed for premedication should be limited to the extent possible. Chronic doses of corticosteroids in excess of 10 mg daily of prednisone or equivalent are prohibited other than for the management of drug-related adverse experiences. Corticosteroid pretreatment should follow the recommended dose and schedule. Steroids may be employed in the treatment of suspected flotetuzumab-associated immunoinflammatory or autoimmune AEs or leukemia-associated AEs in consultation with the Sponsor.
- Use of granulocyte colony stimulating factor or granulocyte-macrophage colony stimulating factor is prohibited during Cycle 1.

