8.2.2 Baseline Disease Characteristics

Baseline disease characteristics will be summarized using descriptive statistics.

- 1. Eastern Cooperative Oncology Group (ECOG) performance status;
- 2. Prior AML therapies;
- 3. Primary induction failure (yes versus no);
- 4. Early relapse (yes versus no), if yes, duration of initial CR (CR1);
- 5. Relapse (yes versus no);
- 6. Initial AML subclassification;
- 7. Genetic and cytogenetics abnormalities at baseline;
- 8. Prior chemotherapy/immunotherapy (not related to study indication, for patients with treatment-related secondary AML) (yes versus no);

- 9. Prior radiotherapy therapies (Not Related to Study Indication, for patients with treatment-related secondary AML) (yes versus no);
- 10. Prior surgery/procedure (Not Related to Study Indication) (yes versus no);
- 11. Bone marrow blasts (%) and category (< 20%; 20% to < 30%; 30% to < 50%; \geq 50%) from the screening bone marrow aspirate sample;
- 12. Peripheral blood blast (%);
- 13. Baseline values of the following lab parameters: hemoglobin, platelet count, absolute neutrophil count (ANC), white blood cells (WBC);
- 14. Number of red blood cell (RBC) transfusions and number of units transfused, and number of platelet transfusions and number of units transfused within 28 days prior to first dose;
- 15. The medical and surgical history will be summarized by the Medical Dictionary for Regulatory Activities (MedDRA) latest version by system organ class (SOC) and preferred term (PT).

8.3 **Prior/Concomitant/Follow-up Medications/Procedures/Therapies**

Prior medications/procedures/transfusions are defined as medications/procedures/transfusions that were started prior to first dose or have start dates missing.

Concomitant medications/procedures/transfusions are defined as non-study medications/procedures/transfusions that are started on or after first dose but before EOTV date or started before the start of the study treatment and ended or remain ongoing during the study treatment. Medication/procedure/transfusion with missing start date but end date on or after first dose date and before EOTV date or with both missing start date and end date is also considered as concomitant medication/procedure/transfusion.

Follow-up medications/transfusions are defined as non-study medications/transfusions that are started after EOTV date.

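### For primary induction failure patients the only baseline marrow can predate permitted salvage and need not show 5% blasts, so a remission from earlier therapy could be scored as a flotetuzumab CR/CRh

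*Protocol*

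**What the plan says.** **Baseline marrow.** Protocol 8.1.1: "Obtain bone marrow aspirate and/or biopsy specimen, if not performed within 30 days before the start of treatment (Cycle 1 Day 1"). Footnote 4 of Appendix 1 repeats the 30-day allowance. SAP 7.1 takes as baseline the latest value at or before first dose, with no condition on therapy given in between.

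**Washout.** Exclusion 6 bars antitumor therapy "within 14 days or 5 half-lives of Cycle 1 Day 1, whichever is longer". Hydroxyurea and other cytoreduction used to bring the blast count down are treated separately in Protocol 6.6 and "should have ceased by the time of first dose of study treatment (Cycle 1 Day 1").

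**Disease status.** PIF is "defined as disease refractory to one of the following, i or ii", where both options are induction or equivalent first-line regimens. Inclusion 3 then permits prior therapy "followed by a maximum of 1 salvage/re-induction attempt". Early relapse (ER) is first "relapse with initial CR1 duration < 6 months". The only numerical blast limit at entry is an upper limit on peripheral blasts (inclusion 6).

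**Endpoint and populations.** CR and CRh (Protocol Appendix 3, SAP Appendix 1) need marrow blasts below 5% plus count thresholds, with no fall from baseline. The primary endpoint is best response of CR or CRh at any time on treatment, judged by the investigator (Protocol 9.6.1, SAP 11.1). The efficacy population has no baseline-marrow condition. The response evaluable population needs a baseline marrow, but sets neither a blast level nor its timing relative to prior therapy.

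**Tabulation.** SAP 8.2.2 lists "Bone marrow blasts (%) and category (< 20"%) as its lowest blast category.

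**The concern.** A marrow taken in the ordinary 14-day screening period falls after the last antitumor regimen, because the washout is at least 14 days (hydroxyurea aside). The 30-day allowance removes that ordering. A PIF patient could have a marrow at about Day -30, receive short half-life salvage, complete the washout and start flotetuzumab with no marrow after the salvage. PIF status was fixed by the earlier induction failure, and no entry rule asks for marrow disease to be shown again.

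Because CR/CRh is absolute, such a patient needs only blasts below 5% and recovered counts at a later assessment, whichever drug produced them. The same holds for a PIF patient whose baseline marrow is already below 5%.

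The trial is single-arm and tested against a fixed 14.7%. No control arm would share this carry-over, and it acts only upward on the primary endpoint.

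**Working it through.** **1. Reproduce the plan's figures.** Inputs (Protocol 9.1, SAP 4.2): continue if at least 5/40; continue if at least 15/100; success if at least 25/100 or at least 35/170. With independent X1 ~ Bin(40, p), X2 ~ Bin(60, p), X3 ~ Bin(70, p):

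P(success) = P(X1 ≥ 5, X1+X2 ≥ 25) + Σ over x = 15 to 24 of P(X1 ≥ 5, X1+X2 = x) · P(X3 ≥ 35 − x).

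| Quantity | Stated | Recomputed |
|---|---|---|
| Alpha at second interim, p = 0.147 | 0.005 | 0.0047 |
| Overall alpha, p = 0.147 | 0.024 | 0.0239 |
| Early futility stop, p = 0.147 | 55% | 28.1% + 26.5% = 54.6% |
| Power, p = 0.23 | about 80% | 78.7% (80.1% if futility is non-binding) |

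The design arithmetic is sound. Overall alpha sits just under the 0.025 limit.

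**2. Does the ordering gap exist?** The 14-day term governs when 5 half-lives ≤ 14 days, so half-life ≤ 14/5 = 2.8 days. For such agents the last permitted day is about Day -15. The accepted marrow may date from Day -30, which leaves Day -30 to Day -15 (16 days) in which therapy can follow the only baseline marrow. For longer half-lives the gap narrows. It closes when 5 half-lives reach 30 days, that is, at a half-life of 30/5 = 6 days.

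**3. Who is affected?** Protocol Appendix 3 defines relapse as at least 5% marrow blasts with blasts reappearing in blood, so ER status carries an implied minimum. PIF does not.

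**4. What would it do to the test?** The documents give no value for f, the share of enrolled patients carrying a remission from earlier therapy. It is an assumption, shown as a range. If all such patients score CR/CRh and the rest respond at p0:

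p = p0(1 − f) + f. For example, p0 = 0.147 and f = 0.02 give 0.14406 + 0.02 = 0.16406.

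| f | Patients of 170 | p, p0 = 14.7% | P(success) | p, p0 = 11.8% | P(success) |
|---|---|---|---|---|---|
| 0 | 0 | 0.147 | 2.4% | 0.118 | 0.1% |
| 1% | 1.7 | 0.156 | 4.8% | 0.127 | 0.3% |
| 2% | 3.4 | 0.164 | 8.9% | 0.136 | 0.8% |
| 3% | 5.1 | 0.173 | 14.7% | 0.144 | 1.9% |
| 5% | 8.5 | 0.190 | 32.0% | 0.162 | 7.8% |

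The 11.8% row base is the meta-analysis point estimate (Protocol 9.1, SAP 4.2); 14.7% is its upper confidence limit and the null value.

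**5. Partial scoring.** If only half of these patients score CR/CRh, p = p0(1 − f) + 0.5f. At p0 = 14.7%, P(success) is then 4.3% (f = 2%), 5.7% (3%) and 9.2% (5%).

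**The case against.** The plan has real safeguards. Registration (Protocol 8.1.2.1) requires dates, outcome, best response and failure for prior treatment, and confirmation of the entry criteria. A disease assessment, CBC with differential and blood flow cytometry fall within 5 days of dosing (8.1.2). The efficacy population requires that PIF or ER was met, and exclusion 18 covers anything that would confound the results. Toxicity recovery to Grade 1 or better and a 2-week ban on growth factors make salvage just before entry harder to fit in. A carried-over remission must also last to an assessment around Day 25 with sufficient counts and, for CRh, no platelet transfusion in the previous 5 days. These points stand. They make a known remission unlikely to pass and argue for a small f, but none documents marrow disease after the last therapy.

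Three stronger readings are tempting and are not supported:

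- That any antileukemic therapy may run to Day -15. The rule is 14 days or 5 half-lives, whichever is longer, so this holds only for short half-lives.
- That no patient needs marrow disease at entry. For ER the relapse definition implies at least 5%, and the open lowest category in SAP 8.2.2 is only a tabulation bin. Blasts of 5 to 19% also fall in it.
- That the true type I error is 9% to 32%. Those values need an f that the documents do not give, full scoring as responders, and a true rate at the null. At 11.8% the chance of success stays below 0.025 up to f = 3%.

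It can also be objected that scoring everyone with a pre-salvage marrow as a non-responder in the primary analysis would bias the rate downward, since some of those salvage attempts will have failed. That is right, and such a rule belongs in a sensitivity analysis.

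**Conclusion.** The gap is in the text but narrow. It concerns PIF patients whose baseline marrow predates short half-life salvage, or whose baseline marrow is already below 5%. Following the plan as written, a remission from earlier therapy in such a patient can enter the primary numerator, and no planned population or analysis removes it.

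Its size is unknown because f is unknown. With a true rate of 14.7%, about 1% of patients (roughly 2 of 170), all scored as responders, is enough to take the chance of success from 2.4% to 4.8%, past the 0.025 limit. With a true rate of 11.8%, the limit is exceeded somewhere between f = 3% and f = 5%. The documents do not show that any such patient has been enrolled.

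**What to change.** - **SAP 11.1, before the efficacy analysis:** state that a patient whose baseline marrow shows fewer than 5% blasts stays in the denominator but is not counted as a CR/CRh responder.
- **SAP 11.1, sensitivity analysis:** pre-specify a CR/CRh analysis that counts as non-responders the patients whose baseline marrow preceded their last antileukemic regimen, hydroxyurea cytoreduction excepted. Describe it as conservative.
- **SAP 8.2.2:** add a below-5% baseline blast category, and tabulate the interval from last therapy to baseline marrow. This would let readers see how large f could be.
- **Future patients:** the sponsor should reconcile the 30-day marrow allowance (Protocol 8.1.1 and Appendix 1 footnote 4) with the washout in exclusion 6, so that the baseline marrow follows the last antileukemic regimen, hydroxyurea excepted.

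The SAP changes need no new procedure, because marrow blast percentages (Protocol 7.14.4) and prior-treatment dates (8.1.2.1) are already collected. For future patients, some could no longer rely on an older marrow. The reported CR/CRh rate may be slightly lower, by an amount that depends on f. The rule should be fixed before the efficacy data are analysed, since adding it later would look data-driven.
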